Statistical Methodology	
Sample size considerations. For this preliminary study, safety analyses are primary. Study termination will occur if, among the 9 treated subjects, there are two cases of wound healing problems or three cases of serious infection, including wound site infection. In the case of a wound site infection, any problems with wound healing will be considered secondary to the infection and NOT as a primary wound healing problem. These estimates are based on neurosurgical experience and reports with the frequency of wound healing problems of <math><2\%</math> and infection from 1.6 to 8.6% in published series, with a mean infection rate of 5.3%.
 
For the analysis of S6 phosphorylation, based on a 2 sample 2 sided t- test, we can detect a difference of <math> 1.4  -  1.5 </math> standard deviations between the comparison controls and the treated group with 9 treated subjects with alpha =0.05 and power of 80%. Preliminary data using quantitative Western blots obtained from 4 resected tubers demonstrated phospho-S6/S6 ratios of 257±42% of control. With 9 treated subjects, and 12 controls we would be able to detect a 64 – 65% difference in phospho-S6/S6 levels between treated and untreated groups, which is likely a biologically meaningful difference.

CONFIDENTIAL

This document and information is the property of the NYU School of Medicine and Langone Medical Center. Do not disclose or use except as authorized in writing by the study IND sponsor

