#### **4.4 Early Withdrawal of Subjects**

##### **4.4.1 When and How to Withdraw Subjects**

A subject may withdraw from the study due to:

- 1) Improvement in seizure activity to an extent that the patient and/or parents/legal guardians elect to forego epilepsy surgery for treatment with everolimus,
- 2) Difficult complying with protocol requirements or
- 3) A decision to withdrawal for personal reasons or adverse effects that are less severe than those that lead to mandatory discontinuation of the treatment phase.

A subject will be withdrawn from the study if any of the following are present:

- 1) The subject develops a systemic bacterial or fungal infection.
- 2) The subject develops a CTAE grade 3 or 4 (severe) event.
- 3) The patient and study will be terminated if he or she is the second case of impaired surgical wound healing or the third case of serious infection, including infection of the wound site, among the 18 everolimus-treated patients.

Given the short duration of treatment, there are no known or postulated safety concerns related to abrupt discontinuation after this duration and dosage of therapy with everolimus. Any subject who elects to withdraw from the study will be recommended to discontinue the everolimus therapy, but if they desire a tapering schedule, one will be provided with exception for those patients going forward with surgery, when everolimus will be completely discontinued prior to surgery.

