## **6 Statistical Plan**

### **6.1 Sample Size Determination**

#### **Statistical Methods**

Distributions of patient and disease characteristics will be summarized descriptively at study entry by dose duration cohort and across cohorts in the everolimus group and in the comparison group. Frequency distributions and cross tabulations will be presented for categorical variables. For continuous variables, summary statistics (means, medians, interquartile ranges, standard deviations, etc) will be provided along with graphical displays (e.g., boxplots) by treatment group.

Safety will be summarized within and across dose duration cohorts and compared with the events in the comparison group.

S6 phosphorylation levels in brain tissue sample at surgery will be summarized descriptively for each dose duration cohort and across cohorts in the treated group and in the comparison group. Further, levels will be compared between the treated and comparison group using 2 sample 2 sided t-tests (with appropriate transformations of levels if required to meet the assumptions of the method).

Similar analyses will be carried out for all additional continuous endpoints of interest. No adjustments for multiplicity will be made in this small study. Bivariate scatterplots and correlation coefficients will also be provided to examine the associations between the multiple endpoints.

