#### **7.3 Subject Population(s) for Analysis**

All patients who receive one or more doses of drug will be included in the analyses of safety. Those patients who undergo surgery will be included in the analyses of S6 phosphorylation and other measurements obtained at the time of surgery. Additional analyses will be conducted to compare those subjects who did not complete treatment and surgery with respect to disease and patient characteristics to identify any potential differences between these groups of patients.

7. Sample size considerations. For this preliminary study, safety analyses are primary. Study termination will occur if, among the 9 treated subjects, there are two cases of wound healing problems or three cases of serious infection, including wound site infection. In the case of a wound site infection, any problems with wound healing will be considered secondary to the infection and NOT as a primary wound healing problem. These estimates are based on neurosurgical experience and reports with the frequency of wound healing problems of <2% and infection from 1.6 to 8.6% in six published series, with a mean infection rate of 5.3%. [33-38]

For the analysis of S6 phosphorylation, based on a 2 sample 2 sided t-test, we can detect a difference of  $|1.4| - |1.5|$  standard deviations between the comparison controls and the treated group with 9 treated subjects with alpha = 0.05 and power of 80%. Preliminary data using quantitative Western blots obtained from 4 resected tubers demonstrated phospho-S6/S6 ratios of 257 ± 42% of control. With 9 treated subjects, and 12 controls, we would be able to detect a 62 – 65% difference in phospho-S6/S6 levels between treated and untreated groups, which is likely a biologically meaningful difference. Prior studies in murine models of TSC treated with rapamycin have demonstrated 90% reduction in phospho-S6 levels [ref]

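### The plan gives two different detectable S6 differences for the same 9 treated and 12 control patients, and neither follows from the stated t-test

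*Combined protocol and SAP*

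**What the plan says.** The Study Summary (Statistical Methodology) and the sample size paragraph in section 7.3 carry almost the same text. Both specify a two-sided two-sample t-test at alpha 0.05 with 80% power, and both first state a detectable difference of 1.4–1.5 "standard deviations between the comparison controls and the treated group with 9 treated subjects with alpha = 0.05 and power of 80"%. That sentence gives no number of controls.

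Both then cite preliminary Western blot data from 4 resected tubers, with "phospho-S6/S6 ratios of 257 ± 42% of control". They convert to the ratio scale for 9 treated and 12 controls, and here they part:

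- Study Summary: "we would be able to detect a 64 – 65% difference in phospho-S6/S6 levels".
- Section 7.3: "we would be able to detect a 62 – 65% difference in phospho-S6/S6 levels between treated and untreated groups".

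Section 7.3 adds a comparison: "Prior studies in murine models of TSC treated with rapamycin have demonstrated 90% reduction in phospho-S6 levels".

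The analysis text (Statistical Methods, section 6.1) plans the same t-test, "with appropriate transformations of levels if required to meet the assumptions of the method". On the analysis set, section 7.3 says: "Those patients who undergo surgery will be included in the analyses of S6 phosphorylation". Section 4.4.1 allows treated patients to "elect to forego epilepsy surgery for treatment with everolimus". No allowance for unevaluable patients is stated.

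**The concern.** The same test, alpha, power, arm sizes and preliminary data cannot yield two detectable differences. Both passages are current text, so neither supersedes the other. The 1.4–1.5 SD also looks too large for 9 versus 12, and multiplying it by 42 matches neither percentage range.

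Reduced S6 phosphorylation is the second primary objective (sections 2.1 and 3.2), and this is its only power statement. The same paragraph calls the detectable difference likely to be biologically meaningful. A reader can judge that only by knowing which figure is meant, whether the ± value is an SD or an SEM, and whether the percentage is in percent-of-control points or is a relative reduction. The last matters because the 90% fall in mice, cited straight afterwards, is a relative figure.

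**Working it through.** **Inputs.** From section 7.3 and the Study Summary: n₁ = 9 treated, n₂ = 12 controls, two-sided alpha 0.05, power 80%, preliminary ratio 257 ± 42 from 4 tubers. Assumed here because the plan does not say: equal variances and all 21 patients evaluable.

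**1. The plan's own conversion.** Taking 42 as an SD:

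- 1.4 × 42 = 58.8 and 1.5 × 42 = 63.0, so the stated SD range corresponds to 58.8–63.0 points. This is neither 62–65 nor 64–65.
- Backwards, 62/42 = 1.48, 64/42 = 1.52 and 65/42 = 1.55 SD.

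**2. The stated test.** Power = P(|T| > t₀.₉₇₅,df), where T is noncentral t with df = n₁ + n₂ − 2 = 19 and noncentrality d·√(n₁n₂/(n₁+n₂)) = d·√(108/21) = 2.268d. The critical value is 2.093. Solving for 80% power gives **d = 1.302 SD**. The normal approximation, (1.960 + 0.842)·√(1/9 + 1/12), gives 1.235, further still from 1.4–1.5.

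**3. Conversion of 1.302 SD to the ratio scale.**

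| Reading of 42 | SD | Detectable difference | Relative to 257 |
|---|---|---|---|
| SD | 42 | 1.302 × 42 = 54.7 points | 21% |
| SEM of n = 4 | 42 × √4 = 84 | 1.302 × 84 = 109.4 points | 43% |

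**4. Power of 9 versus 12 at the stated effects.**

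| Stated effect | Power if SD = 42 | Power if SD = 84 |
|---|---|---|
| 62 points | 88.8% | 35.6% |
| 64 points | 90.6% | 37.5% |
| 65 points | 91.4% | 38.5% |

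In SD units, which do not depend on the 42, 1.4 SD has 85.3% power and 1.5 SD has 89.7%.

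**5. Could rounding explain it?** Read as rounded values, 1.4–1.5 covers 1.35–1.55 SD, or 56.7–65.1 points at SD 42. The correct 1.302 SD lies outside; 1.35 SD already has 82.7% power.

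**6. Could a relative reduction explain it?** 62–65% of 257 is 159–167 points. That is 3.8–4.0 SD at SD 42 or 1.9–2.0 SD at SD 84. Neither is 1.30, nor 1.4–1.5.

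**7. Which arm sizes would give 1.4–1.5 SD at 80% power?**

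| Treated v control | Detectable SD | Points at SD 42 |
|---|---|---|
| 9 v 12 (as stated) | 1.302 | 54.7 |
| 9 v 10 | 1.366 | 57.4 |
| 9 v 9 | 1.407 | 59.1 |
| 9 v 8 | 1.457 | 61.2 |
| 9 v 7 | 1.519 | 63.8 |
| 8 v 12 | 1.352 | 56.8 |
| 7 v 12 | 1.414 | 59.4 |
| 6 v 12 | 1.492 | 62.7 |

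So 1.4–1.5 SD could come from fewer controls or from fewer evaluable treated patients. The documents do not say which, if either.

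**8. Other variants at 9 versus 12 (points at SD 42).** A one-sided test gives 1.138 SD (47.8 points). Alpha 0.025 gives 1.457 SD (61.2 points). 90% power gives 1.508 SD (63.3 points). A simulated Mann–Whitney test needs about 1.35 SD (about 57 points). None of them keeps the stated inputs, and none gives 62–65 or 64–65.

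**The case against.** The best defence is that, if 42 is an SD, the plan's claims are true though not tight: 9 versus 12 detects 1.4–1.5 SD, or 62–65 points, with more than 80% power. The plan also appears to use 42 as an SD, since 62/42 and 65/42 are near 1.5, whereas SD 84 would turn 1.4–1.5 SD into 118–126 points. This is an open-label pilot that calls its safety analyses primary and reports that enrolment fell short because of recruitment difficulty. The literal conflict is a single lower bound, 62 against 64.

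Much of this stands. The error is conservative on that reading, no extra patients are called for, and the SEM case is a question to settle, not a demonstrated loss of power. How the plan used the 42 does not, however, show what the preliminary data reported.

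It can also be said that 1.4–1.5 SD quietly allows for patients without tissue, since 8, 7 or 6 treated against 12 controls give 1.35, 1.41 and 1.49 SD. That is possible, but the sentence names 9 treated and states no allowance. Nor would it reconcile the two percentage ranges.

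Finally, percent-of-control points are the natural unit after 257 ± 42% of control. That is a fair reading, and labelling the unit is a clarification, not a correction.

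**Conclusion.** The concern holds. Two current passages give different detectable differences from identical inputs; that needs no assumption. Under the stated test the detectable difference is 1.30 SD, assuming equal variances and 21 evaluable patients, so the stated 1.4–1.5 SD and both percentage ranges are wrong as the 80%-power figures for 9 versus 12.

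The practical size depends on the 42. As an SD, the design is somewhat better than claimed. As an SEM, the stated 62–65 points would be well out of reach at 80% power. In either case the value rests on 4 tubers and no FCD tissue, so the conversion to points is uncertain. It also applies only if levels are analysed untransformed. The correction should be made, but it is one of consistency and traceability and does not call the arm sizes into question.

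**What to change.** Put one statement in both the Study Summary and section 7.3, for example: *With 9 treated and 12 control patients, all with evaluable tissue, a two-sided two-sample t-test (alpha 0.05, equal variances) has 80% power to detect a difference of 1.30 SD.*

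Then:

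- Check the preliminary data and say whether 42 is an SD or an SEM. Give the matching conversion: about 55 percent-of-control points (21% of 257) for an SD, or about 109 points (43%) for an SEM of 4.
- Label the unit as percent-of-control points, with the relative reduction beside it, and note that the conversion is for untransformed levels and comes from 4 tubers without FCD tissue.
- If 1.4–1.5 SD was meant to allow for patients without evaluable tissue, state the numbers assumed. With SD 42, 8 versus 12 gives 1.35 SD (57 points) and 7 versus 12 gives 1.41 SD (59 points).

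The cost is wording in two places and one look at the source of the 42. Arm sizes and procedures stay as they are.

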## Safety monitoring and reporting

Information about all adverse events, whether volunteered by the subject, discovered by investigator questioning, or detected through physical examination, laboratory test or other means, will be collected and recorded and followed as appropriate.

### **6.2 Adverse events**

#### **6.2.1 Definitions and reporting**

Adverse events that begin or worsen after informed consent should be recorded in the Adverse Events CRF. Conditions that were already present at the time of informed consent should be recorded in the Medical History page of the patient's CRF. Adverse event monitoring should be continued for at least 30 days (or 5 half-lives, whichever is longer) following the last dose of study treatment. Adverse events (including lab abnormalities that constitute AEs) should be described using a diagnosis whenever possible, rather than individual underlying signs and symptoms. When a clear diagnosis cannot be identified, each sign or symptom should be reported as a separate AdverseEvent.

The occurrence of adverse events should be sought by non-directive questioning of the patient at each visit during the study. Adverse events also may be detected when they are volunteered by the patient during or between visits or through physical examination, laboratory test, or other assessments. As far as possible, each adverse event should be evaluated to determine:

1. The severity grade (CTAE Grade 1-4)
2. Its duration (Start and end dates or if continuing at the Safety Follow-up Visit)
3. Its relationship to the study treatment (Reasonable possibility that AE is related: No, Yes)
4. Action taken with respect to study or investigational treatment (none, dose adjusted, temporarily interrupted, permanently discontinued, hospitalized, unknown, not applicable)
5. Whether medication or therapy was given (no concomitant medication/non-drug therapy, concomitant medication/non-drug therapy)
6. Outcome (not recovered/not resolved, recovered/resolved, recovering/resolving, recovered/resolved with sequelae, fatal, unknown)
7. Whether it is serious, where a serious adverse event (SAE) is defined as in Section 8.2.1

All adverse events should be treated appropriately. Such treatment may include changes in study drug treatment including possible interruption or discontinuation, starting or stopping concomitant treatments, changes in the frequency or nature of assessments, hospitalization, or any other medically required intervention. Once an adverse event is detected, it should be followed until its resolution, and assessment should be made at each visit (or more frequently, if necessary) of any changes in severity, the suspected relationship to the study drug, the interventions required to treat it, and the outcome.

Information about common side effects already known about the investigational drug can be found in the [Investigators' Brochure]. This information should be included in the patient informed consent and should be discussed with the patient during the study as needed.

Adverse event monitoring should be continued for at least 30 days following the last dose of study treatment

#### **6.2.2 Laboratory test abnormalities**

Laboratory abnormalities that constitute an Adverse Event in their own right (are considered clinically significant, induce clinical signs or symptoms, require concomitant therapy or require changes in study treatment), should be recorded on the Adverse Events CRF. Whenever possible, a diagnosis, rather than a symptom should be provided (e.g. anemia instead of low hemoglobin). Laboratory abnormalities that meet the criteria for Adverse Events should be followed until they have returned to normal or an adequate explanation of the abnormality is found. When an abnormal laboratory or test result corresponds to a

CONFIDENTIAL

This document and information is the property of the NYU School of Medicine and Langone Medical Center. Do not disclose or use except as authorized in writing by the study IND sponsor

sign/symptom of an already reported adverse event, it is not necessary to separately record the lab/test result as an additional event.

Laboratory abnormalities, that do not meet the definition of an adverse event, should not be reported as adverse events. A Grade 3 or 4 event (severe) as per CTAE does not automatically indicate a SAE unless it meets the definition of serious as defined below and/or as per investigator's discretion. A dose hold or medication for the lab abnormality may be required by the protocol and is still, by definition, an adverse event.

### 6.2.3 Adverse events of special interest (optional)

In clinical trials, everolimus has been associated with serious cases of hepatitis B reactivation, including fatal outcome. Reactivation of infections is an expected event during periods of immunosuppression.

In clinical trials and post-marketing spontaneous reports, everolimus has been associated with renal failure events (including fatal ones) and proteinuria. Renal function will be monitored throughout the study. In clinical trials everolimus has been associated with certain adverse events (Table 6).

Table 6. Specific Adverse Events

Clinically Notable AE grouping	Risk Definition in Risk Management Plan (RMP)	Comment
Amenorrhea	Amenorrhea	Included under potential risk in RMP
Cytopenia	N/A	Included under clinically notable AEs
Hemorrhages	Hemorrhages	Included as important identified risk in the RMP
Hyperglycemia/ new onset of diabetes mellitus	N/A	Included under clinically notable AEs
Hypersensitivity reactions (anaphylactic reaction)	N/A	Included under clinically notable AEs
Infections and infestations	N/A	Included under clinically notable AEs
Intestinal obstruction/ileus	Intestinal obstruction/ileus	Included under potential risk
N/A	Cardiac Failure	Not reported in the MAP. (important identified risk- RMP specific
N/A	Increased creatinine	Please note that this RMP specific identified risk is based on lab data and is defined as newly occurring or worsening increase to CTC grade 3 or 4
Non infectious pneumonitis	Non infectious pneumonitis	Name changed from pulmonary events to non infectious pneumonitis in the MAP. Included under important identified risk in RMP
Rash and similar events	N/A	Not included in the RMP
Renal events	Renal failure/proteinuria	The names in RMP and MAP are different but the search terms are the same. It is included important identified risk in RMP

CONFIDENTIAL

This document and information is the property of the NYU School of Medicine and Langone Medical Center. Do not disclose or use except as authorized in writing by the study IND sponsor

Stomatitis/oral mucositis/ulcers	N/A	Included under clinically notable AEs
Thromboembolism	Thromboembolism	Included as important identified risk in the RMP

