#### **5.3.1 Management of specific toxicities:**

Overall, safety data available from completed, controlled and uncontrolled studies indicate that everolimus is generally well tolerated at weekly or daily dose schedules. The safety profile is characterized by manageable adverse events (AEs). These AEs are generally reversible and non-cumulative.

Adverse events most frequently observed with everolimus are rash, stomatitis/oral mucositis, non-infectious pneumonitis, fatigue, headache, anorexia, nausea, vomiting, diarrhea, and infections. Overall, the most frequently observed laboratory abnormalities include neutropenia, thrombocytopenia, hypercholesterolemia, and/or hypertriglyceridemia. The majority of these AEs have been of mild to moderate severity (NCI CTC grade 1-2). Recommendations for dose adjustments for non-hematologic and hematologic adverse events are summarized in Tables 3 and 4.

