**Table 3: Dosing guidelines for Everolimus-related non-hematologic toxicities**

CONFIDENTIAL

This document and information is the property of the NYU School of Medicine and Langone Medical Center. Do not disclose or use except as authorized in writing by the study IND sponsor

Toxicity	Action
AST or ALT elevation	Maintain current dose level
Grade 1 (> ULN - 3.0 x ULN)	
Grade 2 (> 3.0 - 5.0 x ULN)	
AST or ALT elevation	Interrupt Everolimus administration until resolution to $\leq$ grade 1 (or $\leq$ grade 2 if baseline values were within the range of grade 2). If resolution occurs $\leq$ 7 days, Everolimus should be re-started at the dose level prior to interruption.
Grade 3 (> 5.0 - 20.0 ULN)*	If resolution takes $>$ 7 days, or if event recurs within 21 days, hold Everolimus until recovery to $\leq$ grade 1 or baseline grade/ value and reintroduce Everolimus at one dose level lower, if available.
AST or ALT elevation	Interrupt Everolimus administration until resolution to $\leq$ grade 1 (or $\leq$ grade 2 if baseline values were within the range of grade 2). If resolution occurs $\leq$ 7 days, Everolimus should be re-started at one dose level lower. If resolution takes $>$ 7 days, discontinue Everolimus.
Grade 4 (> 20 x ULN)*	
Recurrence of grade 4 after dose reduction or toxicity requiring Everolimus interruption for $>$ 21 days	Discontinue Everolimus.
Intolerable grade 2 mucositis, or grade 3 AE, except hyperglycemia or hypertriglyceridemia or hypercholesterolemia	Interrupt Everolimus administration until resolution to $\leq$ grade 1 or baseline grade / value. If resolution occurs within $\leq$ 7 days, Everolimus should be re-started at the dose level prior to interruption. If resolution takes $>$ 7 days, or if event recurs within 21 days, hold Everolimus until recovery to $\leq$ grade 1 or baseline grade/ value and reintroduce Everolimus at one dose level lower, if available. Patients will be withdrawn from the study if they fail to recover to $\square$ grade 1 or baseline grade / value within 21 days.
Any other grade 4	Hold Everolimus until recovery to grade $\square$ 1 or baseline value Reintroduce Everolimus at one dose level lower, if available.
Grade 3 or 4 clinical liver failure (asterixis or encephalopathy/coma)	Discontinue Everolimus

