#### **5.3.1.4. Management of hyperlipidemia and hyperglycemia**

Treatment of hyperlipidemia should take into account the pre-treatment status and dietary habits of the patient. Grade 2 or higher hypercholesterolemia ( $>300$  mg/dL or  $7.75$  mmol/L) or grade 2 hypertriglyceridemia or higher ( $>2.5$  times upper normal limit) should be treated with a 3-hydroxy-3-methyl- glutaryl (HMG)-CoA reductase inhibitor (e.g. atorvastatin, pravastatin, fluvastatin) or appropriate triglyceride-lowering medication, in addition to diet.

Note: Concomitant therapy with fibrates and an HMG-CoA reductase inhibitor is associated with an increased risk of a rare but serious skeletal muscle toxicity manifested by rhabdomyolysis, markedly elevated creatine phosphokinase (CPK) levels and myoglobinuria, acute renal failure and sometimes death. The risk versus benefit of using this therapy should be determined for individual patients based on their risk of cardiovascular complications of hyperlipidemia.

Hyperglycemia has been reported in clinical trials. Monitoring of fasting serum glucose is recommended prior to the start of everolimus and periodically thereafter. Patients with diabetes mellitus will be excluded from the study.

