  - They will be instructed on the dosage and administration times of the study medication. All subjects will receive a specific quantity of tablets and they will be asked to record the time that each dose is given. They will be asked to bring back the medication that was not used so it can be reconciled with expected number of tablets to be used. This reconciliation will be logged on the drug reconciliation form, and signed and dated by the study team

6.2a Visit 2a – For patients taking the Everolimus for 3 weeks, at NYU CEC, they will have serum levels of everolimus drawn after 10-12 days on the medication. A trough level will be obtained. The study nurse or doctor will contact the patient with the results when available and will adjust the dose as described above. The nurse or doctor will also ask the patient to report any adverse events.

For active patients who reside outside of the NYC area and are unable to arrive at NYU CEC due to distance and travel issues prior to pre-admission testing, Visits 1 and 2 will be combined as one visit to be completed at least 7 days prior to Visit 3. For these patients with a combined Visit 1 and 2, this could mean a treatment window of 7-21 days depending both on which cohort they are in and how soon they can begin treatment.

Pre-surgical evaluation: Visit 2- Control Group

- Recent history will be reviewed for any change in medical status or change in intake of prescribed or over-the-counter medication.

CONFIDENTIAL

This document and information is the property of the NYU School of Medicine and Langone Medical Center. Do not disclose or use except as authorized in writing by the study IND sponsor

- Vital signs, physical and neurological examination
- A detailed seizure history during the prior week.
- Medication reconciliation.

Blood work: (pre surgical eval) CBC and C-reactive protein(CRP).

For control patients who reside outside of the NYC area and are unable to arrive at the study site due to distance and travel issues prior to pre-admission testing, Visits 1 and 2 will be combined as one visit and can be completed one day prior to Visit 3 if not earlier.

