**6. Stopping rules and criteria for withdrawal of subjects**

Subjects may withdraw from the study at the request of the parent or legal guardian for side effects that impair function or quality-of-life, assuming they do not want to lower the dose to a tolerable range. Subjects will also have drug discontinued by investigator if any serious adverse effect is identified and considered as a possible or definite result of the study medication. These include rash, other signs of hypersensitivity, or liver function tests that exceed baseline or normal measures by 50%. Clinical judgment will be used when determining need for everolimus therapy to be terminated. Other reasons for withdrawal include non-compliance with study procedures, seizure exacerbation, or interaction with current concomitant AED therapy. The method termination of everolimus therapy will be determined based on type of reaction and/or reason for withdrawal.

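### No scheduled blood draw after dosing starts includes renal, liver or metabolic chemistry, although safety is the primary analysis and several safety rules act on those results

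*Combined protocol and SAP*

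**What the plan says.** Several sections of the protocol depend on chemistry results once everolimus has started:

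- **Renal.** Section 6.2.3 states "Renal function will be monitored throughout the study". The increased-creatinine row of Table 6 describes a risk that is "based on lab data and is defined as newly occurring or worsening increase to CTC grade 3 or 4".
- **Liver.** Table 3 gives dose actions by grade for "AST or ALT elevation". The Data Safety Monitoring Plan in section 7.1 (item 6) stops drug for serious effects possibly or definitely due to it, and lists among these "liver function tests that exceed baseline or normal measures by 50" percent.
- **Metabolic.** Section 5.3.1.4 calls for treatment of "Grade 2 or higher hypercholesterolemia" or of raised triglycerides. It adds that "Monitoring of fasting serum glucose is recommended prior to the start of everolimus and periodically thereafter", without naming a visit.
- **General.** Section 4.4.1 withdraws any subject with a grade 3 or 4 event, and section 5.3 ends dosing for one.

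The sample size considerations in the Statistical Plan make safety the primary analysis. Creatinine, bilirubin, AST/ALT and fasting lipids appear as eligibility criteria in section 4.1, before dosing.

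**The concern.** These rules can act only on results that someone obtains. If the schedule is followed as written, the liver-test stop, the creatinine risk and the grade 3-4 withdrawal rule (for chemistry events) have no planned measurement behind them.

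Three things follow for an abnormality without symptoms. The patient is not withdrawn as section 4.4.1 requires and may go to neurosurgery with no on-treatment renal or liver result. The event is missing from the safety summary. It may also be treated as no event when the investigators decide whether to lengthen treatment from 7 to 14 to 21 days.

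That last effect depends on a definition the plan leaves open. The patient-number columns of Table 2 count grade 3-4 events as well as serious ones, whereas the later sentences of section 5.2 count serious adverse events. Section 6.2.2 says a grade 3-4 result is not automatically serious.

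**Working it through.** **Step 1: list every blood timepoint specified after the first dose.**

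| Timepoint | Section | Who | Tests named | Chemistry? |
|---|---|---|---|---|
| Days 10-12 (Visit 2a) | 6.2a | 3-week patients only | Everolimus trough | No |
| 7-21 days after start | 6.5, Medical Monitoring | Treated patients | Blood count with differential, CRP | No |
| Morning of surgery (Visit 3) | 5.9 | Treated patients | Everolimus level, cytokines, mTOR activity; frozen for later batch assay | No |
| 3-10 days after discharge | 6.5 | Treated patients | Blood count with differential, CRP | No |
| 3 weeks after surgery | 6.5 | Only with evidence of infection | Same | No |
| 6 weeks after surgery | 6.5 | Only with evidence of infection | Same | No |

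For Visit 2a the protocol says only that "they will have serum levels of everolimus drawn after 10-12 days on the medication" and that this is a trough. Visits 4, 5b and 6 list no blood tests. The Visit 2 draw, when drug is handed out, is also a blood count and CRP. The count is 0 of 6. The 7-21 day draw may fall on the morning of surgery, so a patient outside the 3-week cohort with no sign of infection may have only two distinct draws. Neither would include chemistry.

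**Step 2: what the blood count can and cannot show.** Section 5.3.1 says "the most frequently observed laboratory abnormalities include neutropenia, thrombocytopenia, hypercholesterolemia, and/or hypertriglyceridemia". The first two are on a blood count, which also serves the Table 4 rules. The two lipid abnormalities are not, so 2 of these 4 are outside the scheduled tests, along with all liver, renal and glucose results.

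**Step 3: what zero events would mean.** With all 9 treated patients tested and no grade 3-4 chemistry event, the exact one-sided 95% upper bound solves (1 − p)^9 = 0.05:

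p = 1 − 0.05^(1/9) = 0.283.

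With no test, zero observed silent events is certain whatever the true rate, so no bound follows.

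**Step 4: effect on escalation.** The documents give no grade 3-4 chemistry rate, so the rates below are assumptions for illustration. Under the section 5.2 narrative, a duration level escalates with 0 events in 3 patients, or with 1 in the first 3 and 0 in the next 3. If detected chemistry events counted:

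P(escalate) = (1 − p)^3 + 3p(1 − p)^2 × (1 − p)^3 = (1 − p)^3 + 3p(1 − p)^5

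The chance of at least one event among 9 patients is 1 − (1 − p)^9.

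| Assumed rate p | At least 1 event in 9 | Escalate if detected | Escalate if undetected |
|---|---|---|---|
| 2% | 0.166 | 0.941 + 0.054 = 0.995 | 1.000 |
| 5% | 0.370 | 0.857 + 0.116 = 0.973 | 1.000 |
| 10% | 0.613 | 0.729 + 0.177 = 0.906 | 1.000 |

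The last column considers chemistry events alone. Over this range missing them changes the escalation probability by 0.005 to 0.094. The larger loss is in individual patient safety and in the safety summary.

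**The case against.** The strongest reply is that this is missing visit-level detail, not missing monitoring. Section 6.2.3 commits to renal monitoring, section 5.3.1.4 recommends periodic glucose, section 6.2.1 records adverse events found by laboratory test, and section 6.8.1 asks for laboratory reports. The section 6.5 draws are labelled as infection surveillance, so a blood count and CRP suit their purpose, and hospitals may run perioperative chemistry anyway.

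This does not close the gap. The renal sentence names no test or visit, and the glucose text is a recommendation. Section 6.2.1 records what is found but schedules nothing. The section 6.8.1 reports are due within 48 hours or two weeks of registration and name no test. Hospital chemistry is neither required nor specified as study safety data. The infection label is fair, but no other section supplies the missing panel.

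The second reply is that the risk is small. Exposure lasts 7-21 days at standard doses. Section 6.5 does not expect dose-limiting toxicity. Section 1.4 cites a preoperative rapamycin trial in glioblastoma with no grade 3-4 toxicity before or around surgery. The sample size text turns directly to wound healing and infection, whose stopping rule is unaffected. Most of this stands, and it limits the severity. It does not explain why the protocol writes rules on liver, renal and lipid results and then schedules no test to feed them.

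It is also true that Table 6 describes the drug's risk management plan and does not define a study endpoint, that three of the six timepoints are conditional or limited to one cohort, and that 28.3% is the bound for any zero of nine.

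**Conclusion.** The concern holds. No specified post-dose draw includes chemistry, while sections 4.4.1, 5.3.1.4, 6.2.3, 7.1 and Table 3 all rely on it or act on it. The gap is confined to renal, liver and metabolic chemistry, because the blood count covers the cytopenias.

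The consequence is that silent grade 3-4 chemistry events may go undetected and that zero events in 9 untested patients would say nothing about their rate. The effect on escalation is modest at the assumed rates of 2% to 10%, and applies only if such events count under the rule used. Absolute risk may be low. The change should be made because it is cheap and the study's primary analysis is safety, but nothing here invalidates the design.

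**What to change.** 1. Add AST/ALT, bilirubin, creatinine, glucose and lipids for treated patients to three planned draws: the one 7-21 days after starting, Visit 2a in the 3-week cohort, and the one 3-10 days after discharge.
2. Require the on-treatment result to be read before surgery, on the same day if the draw falls on the morning of surgery, and before each escalation decision.
3. Use the section 4.1 eligibility values as baseline, together with the pre-dose fasting glucose that section 5.3.1.4 recommends. The lipid criterion is qualified as applying only where applicable, so make pre-dose lipids mandatory.
4. State in section 5.2 whether grade 3-4 events or only serious adverse events govern escalation. Align the cohort 1 size after one event, which is 9 in Table 2 and up to 6 in the narrative.

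The cost is a small assay charge on blood already being drawn, with no new visits. In the 7- and 14-day cohorts these results would inform readiness for surgery, escalation and safety reporting, but would come too late to guide dosing under Table 3. That would need an extra mid-course draw, which is harder for patients who live far away.
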